Family member study partners are the primary participants in this study and the primary outcome is family member-reported quality of communication. We anticipate that few patients will be well enough to participate or have decision making capacity (DMC). If a patient meets the eligibility criteria, study staff will approach the enrolled provider caring for the patient to confirm eligibility. A research team member will check in the patient's chart or with their care team as to whether the patient is intubated. If they are intubated, the research team member will proceed as though they do not have DMC. For non-intubated patients, a member of the research team will check the patient's chart or ask a member of the care team to determine whether capacity has already been assessed. If there remains a possibility a potential subject has limited cognitive abilities, a qualified member of the study team (MD) will determine the patient's decision-making capacity and need for a representative.

If the patient is deemed eligible and is found to lack DMC, a member of the patient's treating team will approach or contact an individual who is consenting on behalf of the subject for other medical procedures (formal or informally designated decision maker), and ask if they would be willing to speak with study staff. A member of the study team may also approach a patient or individual who is consenting on behalf of the patient at the OHSU site. The patient's representative will consent for the patient to participate in this study. We anticipate that many eligible patients will lack DMC. Adult subjects are commonly sedated and/or intubated upon admission and may remain so for much of their initial inpatient course. These subjects are of diminished capacity due to alterations in consciousness resulting from injury/illness and/or to medications administered for the purposes of treatment.

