P1: Patient Survey (Only given to patients with DMC)	Survey given to patients with DMC	30 days post-admission	In-person (if patient member available in hospital) Telephone	T-QoL ⁴³
U1: Unit-wide moral distress survey (pre)	Start of study, prior to any patient enrollment	Before best case/worst case training	Anonymous paper survey	MDS-R ⁴⁴ Physician and nurse versions
U2: Unit-wide moral distress survey (post)	End of study, after all intervention patients are enrolled	After best case/worst case training	Anonymous paper survey	MDS-R Physician and nurse versions
Graphic aid photo-documentation	Graphic aid created by surgeon	As close as possible to 24-72 hours after admission	De-identified digital image	N/A

As shown below, research team members at UT-S/PMH and OHSU will administer 2-3 surveys to family member study partners (number dependent upon whether the patient is alive at 30 days). If the patient has DMC at 30 days, they will be contacted for a single survey.

Data Collection Administration

Focus groups:

A skilled focus group facilitator familiar with technical constructs relating to the topic area will lead the focus group discussions. Focus group discussions will last approximately 90 minutes and will include questions on the challenges providers face when talking with family members of older patients with serious traumatic injury about treatment and prognosis. The focus group moderator will also describe a hypothetical patient and ask focus group participants how they might discuss prognosis and treatment options with the patient's family. Participants will then watch a brief video depicting a surgeon describing treatment options to a patient using the best case/worst case communication technique. After viewing the video, the focus group moderator will ask attendees how best case/worst case could be used in their practice. Focus group guide questions are sample questions and in some cases the facilitator may ask follow up questions not included on the guide.

We will give focus group participants a brief exit survey to complete at the conclusion of the focus group. The exit survey will include demographic questions, as well as questions about the participant's professional role and training. The exit survey will not include collection of any identifiers.

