Chart reviews will be conducted at 10 and 30 days after admission by research team members at UT-S/PMH and OHSU. Team members will use the Therapeutic Intervention Scoring System to guide chart data abstraction in order to measure treatment intensity for the first 10 days after injury.⁵¹⁻⁵⁵ We will record the number and duration of life supporting treatments received⁵⁶ within 30 days of admission using six well described data fields: intubation and mechanical ventilation, tracheostomy, feeding tube insertion, hemodialysis, enteral or parenteral nutrition, and cardiopulmonary resuscitation. We will also record measures of high quality palliative care including initiation and timing of palliative care consultation, documentation of care preferences within 48 hours of admission, timing of Do Not Resuscitate orders and discharge to Hospice.⁵⁷ We will collect the following patient-level covariates: Injury Severity Score, GTOS, TRISS for patients age 50-64, pre-existing comorbid illnesses, age, race and ethnicity, gender, insurance status, educational attainment.

Best case/worst case graphic aid retention

[figure not shown]
A coded digital image of the graphic aid that accompanies the communication intervention (labeled only with study ID number) will be archived by research team members at UT-S/PMH and OHSU. This graphic aid is created as part of the intervention and before it is given to the patient's family a member of the research or clinical teams will take a picture of it for archival.

Primary outcomes: **Primary outcome:** The QOC questionnaire⁴⁰ is a 19-item scale with two domains: general communication (8 items) and end-of-life communication (11 items). The instrument is available in patient-specific and family member-specific versions and has acceptable internal consistency and construct validity.

Data analysis plan: The intervention effect, QOC, will be tested in the framework of generalized linear mixed effects models^{58,59} comparing the pre-intervention with post-intervention periods with a treatment dummy variable, surgeon random effect, and site dummy variables to control for site-specific effect. UW analysts will adjust for covariates to increase the

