statistical precision of our treatment effect estimation. Our exploratory analyses will examine other patient endpoints such as intensity of treatment and palliative care received. We will use linear mixed effects models for continuous responses, logistic random effects models for binary responses and log-linear random effect models for count-dependent variables.

Schedule of Events

★ Patient/family will be approached as close as possible to 24-48 hours post-admit (up to 7 days post-injury) and F1/N1 surveys will be conducted as close as possible to 72 hours post-admit.

Incentives

Trauma providers

Focus groups: To compensate participants for their time during the focus groups, each participant will receive \$200 at the completion of the focus group.

Best case/worst case tool training: To encourage surgeons to participate as research subjects in the “Best Case/Worst Case” training session, incentives will be required as the training will take 2 hours of their time. Using incentives with physicians as research subjects is well-documented in the survey-research literature. Participation is significantly more likely with increased remuneration.^{60,61} Previously, about \$250 per physician has proven a successful incentive for our research; this is the amount given to participants in our surgeon focus groups. We will be giving surgeons \$245 for their time so we do not have to collect social security numbers from surgeon participants at OHSU (\$250 is a common limit for collecting social security numbers from research participants). In addition, we will provide refreshments for surgeons who participate in the training sessions at UT-S/PMH and OHSU. Surgeons will receive incentives only for participating in the training as the intervention requires modest effort beyond the usual care surgeons provide to patients.

Trauma provider interviews following best case/worst case tool training: No incentive is provided for those participating in the interview. *Nurse survey:* UT-S/PMH and OHSU research team members will give \$5 to nurses upon completion of each QOC survey.

Moral distress survey: No incentive is provided for those participating in the moral distress survey.

Family members and patients

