Family Member Participant Incentives: OHSU research team members will give family member participants \$15 for completing the first survey and \$10 for the second survey. Family members who complete the third survey will receive an additional \$10 for a maximum incentive of \$35.

UT-S/PMH research team members will give family member participants \$24 for completing the first survey. Incentives given to family members at UT-SW are lower than at OHSU because UT-SW requires researchers to collect social security numbers and use ClinCards for incentives of \$25 or more. To avoid burdening family members by asking for social security numbers and by including the off-putting ClinCard language in their consent form, we have reduced their total incentive.

At both sites, patients will not receive any compensation for participating in this study. If the family member providing surrogate consent for a patient who lacks DMC and the study partner are *not* the same person, only the study partner will receive incentives.

Statistical Considerations

Sample Size

UT-S/PMH and OHSU research team members will sequentially recruit 50 patients in the control and 50 patients in the intervention arms. Power calculation: Based on current available publications, the standard deviation for the QOC measurement is estimated to be around 3.5. Assuming the between doctor variance accounts for 10% of the total variance, we computed power of 84% to detect a medium-large effect of 2.00 points on the QOC scale, and 96% power to detect a large effect of 2.50 QOC points. If the between doctor variance accounts for 30% of the total variance, the power to detect these effects are 92% and 99% respectively.

Analysis

Analysts at UW will test the intervention effect, QOC, in the framework of generalized linear mixed effects models^{58, 59} comparing the pre-intervention with post-intervention periods with a treatment dummy variable, surgeon random effect, and site dummy variables to control for site-specific effect. We will adjust for covariates to increase the statistical precision of our treatment effect estimation. Our exploratory analyses will examine other patient endpoints such as intensity of treatment and palliative care received. We will use linear mixed effects models for continuous responses, logistic random effects models for binary responses and log-linear random effect models for count-dependent variables.

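### The exploratory treatment-intensity endpoints include life support begun before the tool is expected to be used, and nothing in the plan separates it out or adjusts for it

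*Combined protocol and SAP*

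**What the plan says.** The protocol's Chart review section defines two intensity measures with different clocks. TISS guides abstraction "in order to measure treatment intensity for the first 10 days after injury". For life support, "We will record the number and duration of life supporting treatments received" is followed by a window that opens at admission: "within 30 days of admission using six well described data fields: intubation and mechanical ventilation, tracheostomy", then feeding tube, dialysis, nutrition and resuscitation.

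Three other places bear on timing:

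- **Instruments table, graphic aid row:** the diagram is photographed "As close as possible to 24-72 hours after admission". This is the only timing marker for the tool itself.
- **Schedule of Events:** "Patient/family will be approached as close as possible to 24-48 hours post-admit (up to 7 days post-injury".
- **Consent and HIPAA authorization, family members and patients:** "Adult subjects are commonly sedated and/or intubated upon admission and may remain so for much of their initial inpatient course". No percentage is given.

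On adjustment, Chart review says: "We will collect the following patient-level covariates: Injury Severity Score, GTOS, TRISS for patients age 50-64, pre-existing comorbid illnesses", followed by demographic items, insurance and education. Life support at arrival is not on the list. Timing is to be recorded for palliative consultation and do-not-resuscitate orders; no start times are named for the six life-support fields. The Analysis section gives the endpoints their status: "Our exploratory analyses will examine other patient endpoints such as intensity of treatment and palliative care received". The Project Summary places control enrolment in the first year and intervention enrolment in the second.

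**The concern.** The protocol presents treatment intensity as a downstream outcome. Its stated mechanism is that a better conversation helps limit treatments that do not fit the patient's goals. Care given before the conversation is not downstream of it. For a patient intubated on arrival, that intubation is already counted whatever the conversation later achieves.

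Two things are at stake:

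- **Attenuation.** A constant block of early treatment in both arms pulls ratios towards 1 and adds noise.
- **Case mix.** With sequential, non-randomised arms, a difference between years in how many patients arrive on life support becomes part of the endpoint. The early chart data that would reveal this are collected, but only as outcome.

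**Working it through.** **1. The plan's own figures.** The only power figures are for QOC (50 per arm, SD 3.5). Take the within-surgeon SD as 3.5 × √(1 − ρ), with ρ the between-doctor share of variance, a two-sided 5% level (assumed, as none is stated) and a t reference with 98 degrees of freedom.

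- ρ = 10%: SD 3.32; power 84.7% for 2.00 points (stated 84%) and 96.1% for 2.50 (stated 96%).
- ρ = 30%: SD 2.93; power 92.2% (stated 92%) and 98.8% (stated 99%).

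They reproduce. None concerns intensity, so nothing below changes them.

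**2. Window against tool time.** The share of each window that passes before the tool is hours/240 for TISS and hours/720 for life support, taking admission on the day of injury.

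- Tool at 24 hours: 10% of the TISS window and 3.3% of the life-support window.
- Tool at 72 hours: 30% and 10%.

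**3. Initiation (illustration; every rate is assumed).** Let f be the share intubated on arrival and q the later rate among the rest, 40% in controls and 25% with the tool. The intubation field then contributes f + (1 − f)q to the count. Power is for 50 per arm, normal approximation, two-sided 5%, surgeon clustering ignored.

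| f | Control | Tool | Ratio | Power |
|---|---|---|---|---|
| 0% | 40% | 25% | 0.625 | 36% |
| 20% | 52% | 40% | 0.77 | 22% |
| 40% | 64% | 55% | 0.86 | 15% |
| 60% | 76% | 70% | 0.92 | 10% |
| 80% | 88% | 85% | 0.97 | 6% |

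This is one of six fields. The documents support early onset only for sedation and/or intubation.

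**4. Duration and TISS (assumed effects).** With d days before the tool:

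- Eight ventilator days in all, 30% cut afterwards: observed ratio (d + (8 − d) × 0.7)/8, which is 0.74, 0.78 and 0.81 for d = 1, 2, 3, against a true 0.70.
- Ten equal TISS days, 20% cut afterwards: (d + (10 − d) × 0.8)/10, which is 0.82, 0.84 and 0.86, against a true 0.80.

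The loss is smaller here because most of the window can still respond.

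**5. Case mix (assumed).** Suppose the tool does nothing, later intubation is 40% among those at risk in both years, and arrival intubation is 60% in year 1 and 50% in year 2. The recorded rates are 0.60 + 0.40 × 0.40 = 76% and 0.50 + 0.50 × 0.40 = 70%. That 6-point gap equals the diluted real effect in the 60% row of step 3.

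**6. What a landmark analysis recovers.** At f = 60%, 20 patients per arm are at risk. The number of intubations avoided is the same either way: 50 × 0.06 = 3 and 20 × 0.15 = 3. Power for 40% against 25% with 20 per arm is about 17%, against 10% for the undivided field. The gain is mainly an interpretable estimate; power stays low.

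**The case against.** Five points can fairly be made against this.

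- **The photograph is not the exposure.** The 24-72 hour entry is a soft target for archiving the diagram. Group B is defined by the surgeon having been trained, and nothing bars tool use on the first day. This stands. A reader might infer that opening the window at 24 hours would remove no tool effect; the documents do not establish that. If the tool is used earlier, first-day TISS is post-exposure and adjusting for it would remove part of the effect.
- **Severity is measured.** Injury Severity Score, GTOS, TRISS for ages 50-64, comorbidity and age are collected, and the Analysis section plans covariate adjustment. So it would be wrong to say that arrival severity passes into the endpoint uncontrolled. The adjustment sentence follows the QOC model, however, and is not expressly extended to the exploratory endpoints. No listed covariate records arrival life support.
- **The plan records number and duration, not ever-intubated.** This stands. Duration can still change after the tool, so the yes/no illustration shows the worst-affected component.
- **Early treatment falls on both arms.** This stands: the expected result is attenuation, not bias towards the tool. Bias needs a difference between the two years.
- **Admission is a fair common origin.** Controls have no tool-use time, and total burden from admission is a legitimate quantity. That is a reason to keep it, but it does not isolate the part the tool could change.

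**Conclusion.** The point holds for the exploratory intensity endpoints. Their windows open at injury or admission, before the tool is expected to be used, in patients the protocol itself describes as commonly sedated and/or intubated on arrival. Initiation counts are attenuated most, duration and TISS less. A year-to-year shift in arrival life support would also enter the comparison and be only partly captured by the collected scores.

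The size cannot be computed from the documents. The ranges above rest on assumed arrival rates, later rates and effects, and on the 24-72 hour photograph target as a stand-in for tool use.

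The documents do not support two stronger readings: that the primary QOC result is compromised, or that the total from admission is invalid and should be replaced. The change is worth making because it is cheap, but it does not decide the trial.

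**What to change.** For both arms, before intervention data are analysed:

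1. Abstract start and stop times for the six life-support fields, and TISS by day.
2. Flag life support already present at admission and include it as a covariate in the intensity models, stating that covariate adjustment applies to them.
3. Keep the total from admission, and add a pre-specified analysis of treatments newly started, and duration accrued, after a landmark common to both arms. Use 24 hours after admission if the sponsor confirms the tool is not used earlier, with 72 hours as a sensitivity analysis.
4. Use first-24-hour TISS as a covariate only if tool use before 24 hours is ruled out.

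The cost is somewhat more abstraction work; recording duration should already supply many of the times. New-start counts will be smaller, and the landmark analysis is limited to patients alive at the landmark. No patients or visits are added.

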Family members: Family members are the primary participants in this study and the primary outcome is family-reported quality of communication. We anticipate that few patients will be well enough or have decision making capacity (DMC) to participate. Patients will participate with a family member who is present and is a formally or informally designated decision maker. If a patient has DMC, they will be asked by a UT-S/PMH or OHSU research team member to designate a family member to enroll in the study as the “study partner”. Patients cannot be enrolled without a family member study partner as our primary outcome is the family member’s perception of the quality of communication. If a patient lacks DMC, their family member or surrogate decision maker will be identified and approached. In this circumstance, the surrogate decision maker and study partner do not have to be the same person; a surrogate decision maker may provide consent for the patient chart review and re-contact at 30 days if they have regained DMC whereas another family member serving as study partner may participate in the surveys. In this circumstance (where the study partner is the only one to have consented), if the patient is alive at 30 days, the study partner will complete 3 surveys (including the Trauma Quality of Life survey at 30 days). If they are deceased, the study partner will complete the first two surveys only.

Patients:

We will include traumatically injured patients 50 and older admitted to the ICU.

We will include both patients who have or lack DMC, as described in the “Consent and HIPAA Authorization” section. Given the nature of traumatic injury in the study patient population we anticipate few, if any, patients will have DMC.

Exclusion Criteria:

Trauma providers

Focus groups: Potential participants must not be on call at the time of the focus group.

Best case/worst case tool training and subsequent follow up interviews: We will exclude residents who have not had at least 5 years of postgraduate training. We will also exclude care providers who do not directly provide primary trauma care in the ICU. Trauma consultants including for example, neurosurgeons, orthopedic surgeons, otolaryngologists will be excluded from best case/worst case training.

Nurse survey: No exclusion criteria.

Moral distress survey: No exclusion criteria.

Patients and family members

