Patients who decline to participate: No data after patients decline participation will be collected by UT-S/PMH and OHSU research team members, except for reason for non-participation and screening data. Screening data will include gender, race, and ages of individuals as well as GTOS score (and Trauma Injury Severity Score (TRISS) score for patients aged 50-64) and reason for non-participation. We will not record identifiable information such as patient name or medical record number, instead UT-S/PMH and OHSU research team members will assign a unique identifier (such as D001) to this information, to assist us in tracking the number of declines and maintaining accurate data entry. These data will be recorded so that we may determine whether participants (both in the usual care and intervention group) are categorically different than non-participants.

Consent and HIPAA authorization

Trauma providers

Focus groups: Prior to the start of the focus group, the focus group facilitator will give all participants the info sheet. Participants will be provided with ample time to review it and given the opportunity to ask questions.

Best case/worst case tool training: After a surgeon has expressed interest in learning more about the study, UT-S/PMH or OHSU research staff will meet with them in a private meeting space, explain study procedures and obtain written informed consent. Surgeons who enroll will consent to participating in both the training and to having their patients screened and enrolled in the

study, including having family members and nurses answer survey questions regarding their communication. Given high participation by surgeons in our initial study and endorsement from the chief of trauma at both institutions we anticipate the majority of surgeons at each center will participate. Interested physicians will complete written informed consent prior to participating in the control arm and the surgeon training session.

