If a patient lacks DMC their surrogate decision maker will be approached or contacted regarding surrogate consent. This consent process will occur either face-to-face (if the family member providing surrogate consent is available locally) in which case written consent will be collected OR may be provided via phone or web survey (if the family member providing surrogate consent is out of the area), in which case verbal consent or consent via clicking a survey answer will be collected. In cases where the family member providing surrogate consent is not available locally, the first contact with them will always be made via phone, at which time they will be given the option of a verbal consent or web-based consent process.

Table: Consent and enrollment options

Patient has DMC

 • Patient wants to participate • Family member wants to participate as study partner 	Enroll patient and family member

 • Patient wants to participate • Family member does not want to participate as study partner 	Do not enroll in study

 • Patient does not want to participate • Family member wants to participate as study partner 	Do not enroll in study

Patient does not have DMC and LAR/surrogate is bedside

 • LAR wants to participate as both surrogate and study partner 	Enroll LAR as surrogate and study partner

 • LAR does not want to participate as surrogate or study partner and no other family member agrees to be study partner 	Do not enroll in study

 • LAR does not want to participate as surrogate • Another family member agrees to be study partner 	Enroll study partner. Do not enroll LAR/patient (no chart review or P1 data collected)

Patient does not have DMC and LAR/surrogate is not bedside/is out of area

 • LAR wants to participate as surrogate • Bedside family member wants to participate as study partner 	Enroll LAR as surrogate and family member as study partner

 • LAR does not want to participate as surrogate • Bedside family member wants to participate as study partner 	Enroll family member as study partner. Do not enroll LAR/patient (no chart review or P1 data collected)

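### Does covariate adjustment undercut the stated power, given that some families have no chart data and TRISS stops at age 64?

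*Combined protocol and SAP*

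**What the plan says.** **Power.** Statistical Considerations, Sample Size, takes 50 patients per arm, a QOC standard deviation of 3.5 and a 10% between-doctor share of variance: "we computed power of 84% to detect a medium-large effect of 2.00 points on the QOC scale". It gives 96% for 2.50 points, and 92% and 99% for the two effects if the doctor share is 30%. No allowance for loss is stated.

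**Model.** Analysis, in the same chapter, specifies a mixed model for QOC with a before/after indicator, a random surgeon effect and site indicators. It adds: "We will adjust for covariates to increase the statistical precision of our treatment effect estimation". No covariate is named there.

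**Covariate list.** Chart review has the only list: "We will collect the following patient-level covariates: Injury Severity Score, GTOS, TRISS for patients age 50-64, pre-existing comorbid illnesses", followed by age and sociodemographic items, nine in all. The paragraph on patients who decline pairs the two severity scores: "GTOS score (and Trauma Injury Severity Score (TRISS) score for patients aged 50-64".

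**Who supplies data.** Selection of Participants sets the age range: "We will include traumatically injured patients 50 and older admitted to the ICU". It also provides for cases "where the study partner is the only one to have consented", in which the partner still completes the family surveys. Two rows of the table of consent and enrollment options create such cases, one with the surrogate at the bedside ("Enroll study partner. Do not enroll LAR/patient (no chart review or P1 data collected") and one with the surrogate away ("Enroll family member as study partner. Do not enroll LAR/patient (no chart review or P1 data collected").

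**The concern.** A partner-only family can give the primary outcome but none of the chart-derived covariates. A patient aged 65 or over has no TRISS. A standard mixed-model fit drops any record with a missing covariate, and the plan gives no rule for missing covariates. Read with the Chart review list as the model's covariate set, the primary analysis would keep only chart-reviewed patients aged 50-64, well short of the 50 scores per arm behind the power figures.

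At stake would be precision, and also the make-up of the analysed group. In an unrandomised before/after comparison, a covariate choice that decides which families count gives the analyst some discretion over the primary result.

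**Working it through.** **1. Reproduce the stated power.** Inputs from Sample Size: n = 50 per arm, total SD 3.5, doctor share ρ = 0.10 or 0.30, effect δ = 2.00 or 2.50. Alpha is not stated; two-sided 0.05 is assumed. Research Design aims to balance each surgeon's patients across the two periods, so between-doctor variance drops out of the comparison:

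- Residual SD = 3.5 × √(1 − ρ): 3.320 at ρ = 0.10; 2.928 at ρ = 0.30.
- SE = SD × √(2/50) = SD × 0.2: 0.664; 0.586.
- δ/SE: 3.01 and 3.76 at ρ = 0.10; 3.41 and 4.27 at ρ = 0.30.
- Power (noncentral t, 98 df): 84.7% and 96.1%; 92.2% and 98.8%.

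These match the stated 84/96% and 92/99%. Leaving doctor variance in (SD 3.5) gives 81.5% and 94.7% at either ρ, and a one-sided test gives 91.4% for 2.00 points at ρ = 0.10. Neither fits. The arithmetic is right and rests on 50 scores per arm.

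**2. What a loss of records would do.** The documents give no partner-only share, so these losses are assumed. Same formula, δ = 2.00, covariates explaining nothing:

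| Records lost | n per arm | ρ = 0.10 | ρ = 0.30 |
|---|---|---|---|
| 0% | 50 | 84.7% | 92.2% |
| 5% | 47.5 | 82.8% | 90.9% |
| 10% | 45 | 80.7% | 89.3% |
| 20% | 40 | 75.8% | 85.5% |

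For δ = 2.50, a 20% loss still leaves 91.4% and 96.5%. Generalised least squares for the stated model, with 10 to 20 surgeons assumed, gives slightly lower values for 2.00 points: about 80% and 88-89% at 10% loss.

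**3. What adjustment gives back.** The variance of the treatment effect is proportional to (1 − R²)/(1 − p), where p is the share lost and R² the share of residual variance explained. Break-even is R² = p. With R² = 10%, power for 2.00 points at 0, 10 and 20% loss is 88.2, 84.6 and 80.1% (ρ = 0.10), and 94.6, 92.2 and 88.9% (ρ = 0.30).

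**4. The TRISS case.** If TRISS were a separate term and 50% or 30% of patients were aged 50-64 (both assumed), 25 or 15 per arm would remain. The least-squares power is then about 53% or 33-34% at ρ = 0.10, and 60-63% or 37-39% at ρ = 0.30. These figures need a model that the plan does not state.

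**5. Set the sections side by side.**

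- *Collected versus modelled.* Chart review lists items to abstract. Analysis says covariates will be used and names none. Nothing puts all nine, or TRISS, into the QOC model. The list can equally serve the exploratory analyses of treatment intensity and palliative care.
- *What the 50 counts.* Project Summary, Research Design and Sample Size all count patients. The consent table says that in partner-only cases the patient is not enrolled. Taken literally, those families are additional to the 50, and 50 patients per arm with chart consent remain.
- *Covariates available to all.* According to Instruments, the first family survey collects the literacy screener, family demographics and relationship to the patient alongside QOC. Partner-only families complete that survey. The enrolled provider confirms eligibility before consent, so surgeon and site are known without chart review. A precision-adjusted model that keeps every score can be fitted from data already planned.

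**The case for a change.** The strongest reply is that an unnamed covariate set is itself the defect. Partner-only enrolment is a written pathway, not accidental missingness. The screening data kept on decliners sit under a separate number with no described link to a partner's QOC, so they do not fill the gap. Nothing commits the analysts to the family-survey variables. In a before/after design one would also want to adjust for injury severity, which only the chart supplies. And since Selection of Participants makes family members the primary participants, the 50 could be read as families.

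Part of this stands. The covariates are not named, there is no missing-covariate rule, and the unit behind the 50 could be clearer. Those are omissions of detail, not a contradiction between the power figures and the model. No sensible analyst would enter a score collected only at ages 50-64 as a stand-alone term and discard everyone older. Severity-adjusted results can be given for chart-reviewed families alongside an all-family estimate. Making multiple imputation of the whole chart block the primary analysis would be one defensible choice. Adjusting only for covariates that every family can supply is another, and statisticians would differ on which is better.

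**Conclusion.** No change is needed. The stated power is correct for 50 QOC scores per arm, assuming two-sided 0.05 and surgeons contributing to both periods. The conflict appears only if the abstraction list is taken as the model and fitted to complete cases. Under that reading, an assumed 10% loss costs about 3 to 4 points of power for a 2.00-point effect (84.7 to 80.7%; 92.2 to 89.3%), which covariates explaining 10% of residual variance would recover. The real loss cannot be derived from the documents, and it is nil on the literal count of 50 enrolled patients. The much lower figures for the TRISS case depend on an assumed age mix and on a term nowhere planned. What is left is a gap in specification that analysts would fill sensibly with the data the plan already collects.
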